This practice of direct bonding could yield inaccurate placement of even perfectly positioned and contoured brackets created using a digital treatment program. To solve this issue, LFO created a 3D printed patient-specific indirect-bonding (IDB) system. Designed directly from the desired bracket placement on the teeth in malocclusion, like a digital mold, the IDB tray precisely matches the tooth anatomy and brackets. Once printed, the corresponding patient's brackets are placed in the IDB tray's bracket wells. The orthodontist can paste the bonding material onto the brackets, while remaining in their specific wells, then place the IDB trays in the patient's mouth and bond the brackets. Once the tray is removed the brackets remain on the teeth in the exact position they were designed for in the treatment planning system.

The presented investigational testing aims to assess treatment efficiency metrics using the LightForce Orthodontic system on a variety of malocclusions across multiple sites compared to the investigator's past experience using traditional bracket systems.

Investigation Design & Participants

This multi-site investigation will evaluate treatment efficiency metrics of different orthodontists using the same LightForce Orthodontic digital treatment planning system and patient-specific brackets. Data collection will include treatment efficiency metrics, participant data such as (but not limited to) gender, age and medical history, and experiential data of standard bracket treatment efficiency metrics. Efficiency metrics may include:

- Treatment length
- Bonding/De-bonding appointment time length
- Length of time to achieve leveling and alignment
- Number of unscheduled appointment
- Number of debonded brackets
- Number of repositioned brackets

All patients that visit the investigation sites are evaluated during initial consultations for their particular medical needs and orthodontic treatment. If a patient is eligible for the investigation, they will be presented with the treatment plan, asked whether they would like to participate, and given a consent form to sign.

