There are no specific recruitment materials for this study. However, each orthodontist is provided with a LightForce Orthodontics welcome kit before they enroll their first patient. This includes a typodont, a sample product package (box, brackets in trays and arch form) and patient brochures as pictured below. The patient brochures are not included as study recruitment material.

To run statistical analysis, at least 22 patients must participate at each investigation site to have a power of 90% at a 5% significance level. No patients will be withdrawn from the investigation unless the investigator or patient chooses to discontinue treatment. If there is a lack of compliance with the investigator's treatment plan and/or a developing health condition during treatment, the patient's data may be considered an outlier and not used in statistical analysis.

Inclusion Criteria

- All subjects must be healthy and between the ages of 10 and 65.
- Eruption of all permanent teeth excluding second and third molars
- Sufficient labial tooth surface for bonding
- No more than one tooth missing from a single arch quadrant
- No existing molar tubes or bands

Exclusion Criteria

- Presence of systemic diseases, cleft lip and palate, craniofacial anomalies, syndromes affecting bone or teeth, impacted teeth (excluding 3rd molars), and tumors of the parathyroid gland
- Presence of bridges or implants
- Cases requiring orthognathic surgery
- Significant periodontal disease
- Intake of drugs affecting tooth movement or bone formation (chronic use of Non-Steroidal Anti Inflammatory Drugs, bisphosphonates, levothyroxine, or teriparatide drug class)
- Pregnancy

Clinical Process

Orthodontic treatment process through out this investigation will follow standardized practices. Treatment data will be acquired throughout the following process:

- Facial photos and intra-oral scans will be taken of the patient's teeth
- Treatment will be planned using the LightForce Orthodontics' LF Pro treatment planning system
- LightForce Orthodontics will manufacture and ship the patient-specific brackets to the investigator
- Standard Orthodontic Treatment Progressions
 - Brackets will be bonded to patient's teeth
 - Follow up appointments to change ligatures, move through standard wire progression, and/or replace brackets. The number of appointments can vary based on the patient's treatment plan and progress.
 - Brackets are removed

Conflicts of Interest

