The LightForce Orthodontic braces are commercially available in the United States. Every orthodontist in this study will pay LightForce Orthodontics for the LFO System as they would if they were available to purchase in Canada. As such there is no conflict of interest.

However, some investigators are a part of the LightForce Orthodontics' clinical executive board (CEB). If so a [CEB Appendix](#) is attached to their patient's consent form. To also combat any undue influence conflict of interests may have on this study, the investigators chosen are a mix of CEB and non-CEB members. This means any CEB member's data should not influence the overall study

results.

Statistical Analysis

Statistical tests (Student's t-test) will be run to make sure LightForce Orthodontics's Clinical Executive Board (CEB) member treatment group outcomes are not statistically different from non-CEB members within this study. If they are, the data collected from that investigation site will be removed.

We will assume the data will be normally distributed for this study. The primary outcome measures are impacted directly by the patient's age and by the treating orthodontists. Thus the outcome variables will be analyzed through analysis of covariance (ANCOVA) tests controlling for age and orthodontist. Multiple pair wise comparisons may be conducted (t-tests) to determine significant differences between groups. Bonferroni corrections may be conducted to prevent the introduction of Type 1 errors. Multivariate linear regressions may also be used to examine differences in the treatment groups. All statistical tests will be two-sided with a p-value of 0.05 for statistical significance. All statistical analyses will be conducted in a statical software such as SAS software (SAS Institute, Cary, NC).

Risk Assessment

There are no additional risks to participating in this study outside of the standard risks associated with orthodontic treatment. The study does not change the standard method of diagnosis and care for the treatment of malocclusion. The LFO bracket system has been approved by the FDA and is comparable to existing bracket systems. During the approval process, the device underwent standard orthodontic bracket performance tests compared to commercially available devices and biocompatibility tests. These reports can be made available upon request.

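### Bonferroni is the only multiplicity correction named, and it is optional; Holm's step-down method holds the same 5% family-wise error and never rejects less, so naming it is a cheap improvement

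*Combined protocol and SAP*

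**What the plan says.** The Statistical Analysis section plans ANCOVA adjusted for age and orthodontist, then adds: "Multiple pair wise comparisons may be conducted (t-tests) to determine significant differences between groups". The next sentence on multiplicity is "Bonferroni corrections may be conducted to prevent the introduction of Type 1 errors". No other correction appears in the document. Both sentences are permissive. The same section then sets one threshold for everything: "All statistical tests will be two-sided with a p-value of 0.05 for statistical significance".

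The family of tests is not defined. The section speaks of primary outcomes in the plural but does not name them. Investigation Design & Participants lists six metrics under the words "Efficiency metrics may include".

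The only sample-size statement, also in Investigation Design & Participants, is that "at least 22 patients must participate at each investigation site to have a power of 90% at a 5% significance level". It gives no effect size, SD, outcome or test, and no allowance for multiplicity. The LFO results are to be "compared to the investigator's past experience using traditional bracket systems"; no comparator sample size is stated.

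**The concern.** Single-step Bonferroni tests each of m comparisons at 0.05/m. Holm orders the p-values, tests the smallest at 0.05/m, the next at 0.05/(m-1) and so on, and stops at the first failure. Its first threshold equals Bonferroni's and the later ones are larger, so it can only add rejections. It controls family-wise error at 5% under any dependence between the tests, as Bonferroni does.

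Holm gains most when several effects are real. The Hypothesis and Significance sections expect that: the same custom bracket and bonding tray are said to reduce wire bends, bracket replacement and delay to finishing. If a correction is applied and the one named method is used, some real improvements may be missed that an equally valid procedure would have shown.

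**Working it through.** **1. The plan's own figure.** The 22 patients per site cannot be reproduced forwards, because no effect, SD or test is given. Solving backwards for 90% power at two-sided 0.05 (noncentral t) gives these standardised effects:

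- 22 v 22: d = 1.00
- 11 v 11: d = 1.45
- one-sample or paired with 22: d = 0.73

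The 22 v 22 layout with d = 1.0 is used below. It is an assumption and not a figure from the documents.

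**2. Bonferroni power per metric.** Power = P(T > t[1 - alpha/(2m), 2n - 2]), where T is noncentral t with noncentrality d × √(n/2).

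- n = 22, uncorrected: noncentrality 1.0005 × √11 = 3.318, 42 df, critical value 2.018; power 90.0%.
- n = 22, m = 6: critical value 2.769; power 70.6%.
- n = 44, m = 6: noncentrality 1.0005 × √22 = 4.693, 86 df, critical value 2.701; power 97.5%.

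**3. Holm against Bonferroni by simulation.** Six metrics, equal correlation 0 to 0.6, d = 1.0 for each real effect. Average power per real effect:

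| Per group | Real effects | Bonferroni | Holm |
|---|---|---|---|
| 22 | 6 of 6 | about 71% | 81-84% |
| 22 | 3 of 6 | about 71% | about 74% |
| 22 | 1 of 6 | 70.6% | 70.7% |
| 44 | 6 of 6 | 97.5% | 99.3-99.6% |
| 44 | 3 of 6 | 97.5% | about 98% |

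At 22 v 22 with all six effects real, the chance of showing all six is 12-38% with Bonferroni and 49-67% with Holm. The chance of at least one true rejection agrees to within 0.1 point in every setting. Simulated family-wise error was at most 4.9% with either method.

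**4. Smaller families.** At 22 v 22 with every effect real and correlation 0 to 0.5, Bonferroni v Holm is 84% v 88-89% for m = 2 and 79% v 86-88% for m = 3.

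**5. No correction, which the text allows.** Per-metric power stays at 90%. Family-wise error for independent tests is 1 - 0.95^m: 9.8% for m = 2, 14.3% for m = 3 and 26.5% for m = 6.

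**The case against.** **Nothing is committed.** A reader might infer that the plan imposes a correction and so gives up power. It does not: both the pairwise tests and the correction are optional. The larger weakness in that sentence is the opposite one, that type I error is left uncontrolled. This stands. Putting Holm's name in place of Bonferroni's while keeping the correction optional would not cure it. Against an uncorrected analysis, Holm lowers per-metric power from 90% to 81-84% or less under the assumptions above.

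**The family is assumed.** The Bonferroni sentence follows one about comparisons between groups, and may refer to those rather than to six metrics. The metric list is itself provisional. This stands, and it is why the size is given only as a conditional range.

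**Power under correction may not be the limiting factor.** Twenty-two is a minimum per site in a multi-site study, and adjustment for orthodontist suggests pooling. With two sites' worth of patients per arm, the gain is about 2 points or less. The sample-size sentence does state power per site, so a single-site analysis remains possible, but the documents do not settle it.

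**Bonferroni has merits.** It is valid and gives simple simultaneous confidence intervals, so a reader should not infer that it is an error or that its cost buys nothing. The plan mentions no confidence intervals, however, so it does not use that advantage as written.

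**Conclusion.** The point holds as a cheap improvement. Holm's superiority in rejections at the same family-wise error is a mathematical property and does not depend on this trial's data. The size of the benefit does.

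Under the assumed 22 v 22 layout, 1.0 SD effects and six metrics, the benefit runs from about 0.1 point per real effect (one real) to about 10-14 points (all six real). It shrinks to about 2 points or less at 44 v 44. It does not materially alter the chance of finding at least one real effect. The documents do not establish which of these cases applies. They also do not support the stronger inferences that a power loss is already built into the plan or that Bonferroni is a mistake.

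**What to change.** Replace the Bonferroni sentence in the Statistical Analysis section with:

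> P-values for the LFO v traditional contrasts across the listed primary metrics will be adjusted by Holm's step-down method at a family-wise two-sided 5%.

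List those primary metrics in the same section before analysis. Without the list the sentence cannot be applied. Restricting the family to LFO v traditional contrasts keeps comparisons between orthodontists, which the Objective does not ask about, from using up alpha.

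The cost is one sentence and one list; standard software performs the adjustment and no further data are needed. There are two downsides:

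- Simultaneous intervals that match Holm are less simple. Any unadjusted 95% intervals must be labelled as unadjusted, because one can exclude zero while the adjusted test is not significant.
- Compared with applying no correction, per-metric power falls. That is the price of controlling type I error.
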